PET	Positron emission tomography
PIF	Patient information form
PR	Partial response

PSA	Prostate specific antigen
PSMA	Prostate specific membrane antigen
(S)AE	(Serious) Adverse Event
SD	Stable disease
SDC	Salivary duct carcinoma
SPC	Summary of Product Characteristics (in Dutch: officiële productinformatie IB1-tekst)
Sponsor	The sponsor is the party that commissions the organisation or performance of the research, for example a pharmaceutical company, academic hospital, scientific organisation or investigator. A party that provides funding for a study but does not commission it is not regarded as the sponsor, but referred to as a subsidising party.
SPSS	Statistical package for the social sciences
SUSAR	Suspected Unexpected Serious Adverse Reaction
SUV	Standardized uptake value
ULN	Upper limit of normal
Wbp	Personal Data Protection Act (in Dutch: Wet Bescherming Persoonsgegevens)
WMO	Medical Research Involving Human Subjects Act (in Dutch: Wet Medisch-wetenschappelijk Onderzoek met Mensen)

SUMMARY

Rationale: PSMA is a transmembrane protein, which is expressed on prostate cancers cells, ACC and other malignancies. In prostate cancer, distant metastases can be visualized sensitively and non-invasively with ^{68}Ga -PSMA-PET/CT scans and if the uptake of ^{68}Ga is high enough, patients can be treated with the β -emitting radionuclide ^{177}Lu -PSMA. In the current study, we will evaluate the uptake of ^{68}Ga -PSMA by performing ^{68}Ga -PSMA-PET/CT scans in advanced ACC and SDC patients. If the uptake is high enough, this will form the rationale for a therapeutic study with ^{177}Lu -PSMA in ACC and SDC.

Objective: The primary objective is to evaluate the uptake of ^{68}Ga -PSMA in locally advanced, recurrent and metastatic ACC/SDC by performing ^{68}Ga -PSMA-PET/CT scans. The secondary objectives are to calculate the SUV tumor-to-background ratio and tumor-to-‘healthy salivary gland tissue’ ratio. To correlate the SUV to the degree of immunohistochemical PSMA expression of the primary tumor on archival tissue, and to establish whether new metastatic lesions are found by ^{68}Ga -PSMA-PET/CT imaging.

Study design: Diagnostic study which evaluates the level of PSMA expression in ACC/SDC patients with ^{68}Ga -PSMA-PET/CT imaging in order to establish whether these patients are eligible for ^{177}Lu -PSMA therapy.

Study population: Patients with locally advanced, recurrent or metastatic ACC/SDC of ≥ 18 years old.

Main study parameters/endpoints: the main study endpoints are the tumor SUV, the SUV tumor-to-background ratio, the SUV tumor-to-‘healthy salivary gland tissue’ ratio, and the correlation between the SUV and the degree of immunohistochemical PSMA expression of the primary tumor on archival tissue.

Nature and extent of the burden and risks associated with participation, benefit and group relatedness: Participants will undergo ^{68}Ga -PSMA-PET/CT imaging and a venapuncture. These are standard diagnostic procedures with a known minimal safety risk. The participant will be asked to make 2 study related visits, which will take 3 hours in total. A participant will not benefit from participating in this study. The study does not involve minor or incapacitated subjects.

1. INTRODUCTION AND RATIONALE

PSMA is a transmembrane protein. PSMA expression can be visualized and quantified by immunohistochemical staining of tissue biopsies with anti-PSMA monoclonal antibodies.¹ This has been done for numerous healthy and malignant tissues. PSMA expression appears to be restricted to a few healthy tissues, such as the prostate, duodenum, proximal renal tubules, breast and skeletal muscle.² Results on PSMA expression of healthy salivary gland tissue are conflicting.¹⁻⁴ In malignant tissue, PSMA expression was found in prostate cancer cells and the neovasculature of many other solid malignancies, including renal cell carcinoma, bladder cancer, colon cancer, neuroendocrine carcinoma, melanoma, pancreatic cancer, non-small cell lung cancer, breast cancer and others.² In ACC, a study in 54 patients showed PSMA expression in 85% of patients, and in 70% of patients with recurrent ACC.⁵ The level of PSMA expression in SDC is currently under investigation, and the first results show PSMA expression in >80% of patients.

PSMA expression is of increasing importance, as it is a target for cancer diagnostics. After labelling PSMA ligands with ⁶⁸Ga, PSMA expression can be visualized non-invasively with a ⁶⁸Ga-PSMA-PET/CT scan. In a study in 248 patients with a history of prostate cancer who presented with a rising PSA level, it was found that ⁶⁸Ga-PSMA-PET/CT scans visualized substantially more tumor lesions than reported for other imaging modalities, such as CT, ¹⁸F-FDG-PET (figure 1), ¹¹C-choline-PET and MRI.⁶ This demonstrates that radiolabeled PSMA ligands very effectively target prostate cancer lesions in vivo, allowing specific and sensitive detection of prostate cancer lesions with PET.

[figure not shown]

Figure 1. ¹⁸F-FDG-PET scan (left) and ⁶⁸Ga-PSMA-PET scan (right) in a patient with metastatic prostate cancer. The black dots in the abdomen on the right scan represent prostate cancer metastases that could not be visualized by ¹⁸F-FDG-PET.

Next to its diagnostic importance, the efficient and specific targeting of PSMA paved the road to exploring the therapeutic potential of PSMA ligands labeled with β -emitting radionuclides, such as ^{177}Lu . We recently showed that ^{177}Lu -PSMA effectively inhibited the growth of PSMA expressing tumors in a mouse model for prostate cancer.⁷ The first results of radionuclide therapy studies with ^{177}Lu -PSMA in prostate cancer patients who failed conventional therapeutic options have been published recently.⁸⁻¹⁰ The group in Bad Berka in Germany reported the results of the first 56 patients with castration resistant prostate cancer treated with 1-4 cycles of 6,000 MBq ^{177}Lu -PSMA. ^{177}Lu -PSMA showed high, specific and rapid uptake in prostate cancer metastases, with almost complete retention during 1-2 weeks after injection. In these advanced stage patients remarkable therapeutic responses were seen: of 56 patients, 45 (80.4 %) demonstrated a reduction in PSA levels and 31 patients (56%) had a partial response according to EORTC criteria¹¹ (figure 2).

[figure not shown]

Figure 2. Response in castration resistant prostate cancer patients treated with ^{177}Lu -PSMA.⁸

The group in Munich treated 19 patients with metastatic castration resistant prostate cancer with a total of 40 cycles of 7400 MBq of ^{177}Lu -PSMA (1-4 cycles per patient). Only mild side effects were seen in part of the patients: dry mouth (37%), anemia (32%) and thrombocytopenia (25%). Most importantly, marked PSA responses were seen in most patients (44% of patients showed a reduction of $\geq 50\%$). Assessment of bone and soft tissue metastases showed complete remission in 5% of patients (figure 3), stable disease in 63% and progressive disease in 32%.

[figure not shown]

Figure 3. Complete remission in a 71-year-old patient after 4 cycles of ^{177}Lu -PSMA.⁹

In summary, prostate cancer lesions can be targeted efficiently with radiolabeled PSMA ligands. Labeled with ^{68}Ga , PSMA ligands can be used to sensitively detect these tumors noninvasively with PET. Labeled with β -emitting radionuclides such as ^{177}Lu , PSMA ligands are a new class of powerful therapeutics for targeted radionuclide therapy.

In the current study, we will evaluate the uptake of ^{68}Ga -PSMA by performing ^{68}Ga -PSMA-PET/CT scans in locally advanced, recurrent and metastatic ACC/SDC patients. Tumor uptake will be measured quantitatively. The tumor-to-background ratio and tumor-to-‘healthy salivary gland tissue’ ratio will be calculated. Tumor uptake will also be correlated to the degree of immunohistochemical PSMA expression of the primary tumor on archival tissue.

This study is of relevance for patients with locally advanced, recurrent or metastatic ACC/SDC because treatment options are very limited and ^{177}Lu -PSMA could be a promising new treatment option. In prostate cancer, ^{177}Lu -PSMA therapy has proven its value as stated above. In ACC/SDC this therapy may also be effective because PSMA expression in ACC/SDC is observed immunohistochemically and in a case report on ^{68}Ga -PSMA-PET/CT imaging in ACC.¹² In order to establish whether ACC/SDC patients are eligible for ^{177}Lu -PSMA therapy, the level of PSMA expression has to be established with ^{68}Ga -PSMA-PET/CT scans. This is the goal of this study. If this study indeed shows sufficient PSMA expression, a therapeutic study with ^{177}Lu -PSMA will be started in next future.

2. OBJECTIVES

Primary Objective: To evaluate the uptake of ^{68}Ga -PSMA in locally advanced, recurrent and metastatic ACC/SDC by performing ^{68}Ga -PSMA-PET/CT scans.

Secondary Objective(s):

- To calculate the SUV tumor-to-background ratio and tumor-to-'healthy salivary gland tissue' ratio.
- Correlate the tumor uptake (SUV) to the degree of immunohistochemical PSMA expression of the primary tumor on archival tissue.
- To establish whether new metastatic lesions are found by ^{68}Ga -PSMA-PET/CT imaging

3. STUDY DESIGN

Design: diagnostic study which evaluates the level of PSMA expression in ACC/SDC patients with ^{68}Ga -PSMA-PET/CT imaging in order to establish whether these patients are eligible for ^{177}Lu -PSMA therapy.c

Duration: each patients has to make 2 additional visits (apart from normal patient care) when he or she participates in this study. These 2 visits will take approximately 3 hours in total.

Setting: single center study (Radboud university medical center, Nijmegen, the Netherlands)

[figure not shown]

Figure 4. Flow chart of study procedures.

4. STUDY POPULATION

4.1 Population (base)

Study population: Patients with locally advanced, recurrent or metastatic ACC/SDC.

Source population:

- Patients with locally advanced, recurrent or metastatic ACC/SDC who are treated at the Department of Medical Oncology of the Radboudumc.
- Patients with locally advanced, recurrent or metastatic ACC/SDC who heard or read about this study and contact the investigators to ask whether they can take part in the study. Potential participants will not be actively recruited. However, there will be a message on the website of Dutch Salivary Gland Cancer Patient Platform: <http://speekselklierkanker.org/>. This message is added to this submission (see 'E3 Wervingsmateriaal').

As the Radboudumc is the largest clinic and research center for locally advanced, recurrent and metastatic ACC/SDC in the Netherlands, we do not expect problems to recruit 15 ACC and 10 SDC patients.

Feasibility analysis

The Radboud University Medical Center is a tertiary referral center for head and neck cancer and salivary gland cancer in particular, receiving referrals from the other academic medical centers in the Netherlands. In 2016 40 new advanced SGC patients were seen at our outpatient department. In addition, patients who have been under control for longer at our OPD may be included directly from the start of the study. Therefore we believe it is feasible to enroll 15 ACC patients en 10 SDC patients within the relatively short time period of 12 months.

4.2 Inclusion criteria

In order to be eligible to participate in this study, a subject must meet all of the following criteria:

- locally advanced, recurrent or metastatic ACC/SDC
- Age \geq 18 years old
- Ability to provide written informed consent

4.3 Exclusion criteria

A potential subject who meets any of the following criteria will be excluded from participation in this study:

- Contra-indication for PET imaging
 - Pregnancy
 - Breast feeding
 - Severe claustrophobia
- Impaired renal function: MDRD <30 ml/min/1,73 m²
- Impaired liver function: AST and ALT ≥ 2.5 x ULN (≥ 5 x ULN for patients with liver metastases)

4.4 Sample size calculation

The main purpose of this study is to establish the feasibility and value of ⁶⁸Ga-PSMA-PET/CT scans as a non-invasive method to assess PSMA expression in ACC/SDC patients. An exact sample size calculation is not applicable, because baseline information concerning the uptake of ⁶⁸Ga-PSMA in ACC/SDC patients is not available. Therefore we will establish ⁶⁸Ga-PSMA-PET/CT scanning in 15 ACC and 10 SDC patients. If the technique does not prove its value in these patients, we will conclude that it is not a valuable imaging technique for ACC/SDC patients.

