8. METHODS

8.1 Study parameters/endpoints

8.1.1 Main study parameter/endpoint

The SUV of ⁶⁸Ga-PSMA estimated with ⁶⁸GA-PSMA-PET scanning. If the SUV of tumor tissue is higher than the SUV of healthy salivary gland tissue and/or comparable to the SUV in prostate cancer, the level of PSMA expression is deemed high enough to pursue a therapeutic study with ¹⁷⁷Lu-PSMA.

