10.2 Secondary study parameter(s)

Tumor-to-background ratios and tumor-to-'healthy salivary gland tissue' ratios will be calculated using the SUV. It will be presented as mean and standard deviations.

Immunohistochemical PSMA expression on a tissue sample of the primary tumor will be quantified using a four point scale for tumor PSMA expression (0 = no expression, 1 = weak expression, 2 = moderate expression, and 3 = strong expression) and the number of PSMA-positive blood vessels per mm² will be counted.

The correlation between the immunohistochemical PSMA expression and tumor SUV will be evaluated using linear regression analysis. A p-value of <0.05 will be considered significant. Analyses will be performed using SPSS version 22.0.

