11.4 Benefits and risks assessment, group relatedness

Risk assessment: as ^{68}Ga -PSMA-PET/CT imaging is a known diagnostic procedure used for prostate cancer in normal patient care, the risks of this procedure are well known and minimal. Next to this, 30 ml blood will be drawn from the participants by a venapuncture. This risks of this procedure are also well known and minimal.

Benefit assessment: participants will not benefit directly from this study as it is a non-therapeutic trial. If the study is successful, participants may participate in a therapeutic study with ^{177}Lu -PSMA which may be beneficial.

Group relatedness: the study does not involve minors and/or incapacitated subjects

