13. STRUCTURED RISK ANALYSIS

13.1 Potential issues of concern

a. Level of knowledge about mechanism of action

68Ga-PSMA-PET imaging is a specific and sensitive method to target prostate cancer lesions in vivo.⁶ In this study we will investigate its value in patients with salivary gland cancer, i.e. adenoid cystic carcinoma and salivary duct carcinoma. There are several reasons why this could be a valuable imaging modality for these patients. First of all, immunohistochemical PSMA-staining show that most ACC and SDC tumor are PSMA-positive. Second, 68Ga-PSMA-PET scans in prostate cancer patients show uptake of 68Ga-PSMA in the salivary glands. Third, a case report has proved the principle of 68Ga-PSMA-PET imaging in a patient with ACC.¹²

b. Previous exposure of human beings with the test product(s) and/or products with a similar biological mechanism

68Ga-PSMA-PET imaging is an imaging modality which is increasingly being used in recurrent prostate cancer patients.¹³ Because of the wide experience with this imaging modality in prostate cancer patients, the safety is well known, and serious adverse events have never occurred (see also chapter 6.2 in the IB).

c. Can the primary or secondary mechanism be induced in animals and/or in ex-vivo human cell material?

In preclinical studies, excellent PSMA-specific tumor imaging in vivo with high tumor uptake ($3.29 \pm 0.77\%$ ID/g) as well as high tumor-to-blood (22:1) and tumor-to-muscle (122:1 at 120 min p.i.) ratios at 120 min p.i. has been described for the PSMA+ tumors. Next to this, high specific uptake in PSMA+ murine tissues (among others the salivary glands) is observed. More information can be found in the IB (chapter 5: nonclinical studies, page 11).

d. Selectivity of the mechanism to target tissue in animals and/or human beings

PSMA specific imaging is found in animals (see answer to previous question) as well as in prostate cancer patients (IB, chapter 6: clinical studies, page 13).

e. Analysis of potential effect

The safety window is wide, as no serious adverse events have been reported in the literature. See the IB (chapter 6.2 and 7, page 15) for more information.

f. Pharmacokinetic considerations

See the IB, chapter 6.1: Pharmacokinetics and Product Metabolism in Humans, page 13)

g. Study population

Patients with locally advanced, recurrent or metastatic ACC or SDC.

h. Interaction with other products

Not applicable

i. Predictability of effect

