In ACC and SDC, the investigational product has not been evaluated before and is therefore not yet predictable. In this study we will correlate the SUV of the primary tumor with the level of immunohistochemical PSMA staining on archival tissue to establish whether the efficacy of PSMA-PET imaging can be predicted with immunohistochemistry.

j. Can effects be managed?

No side effects which require to be managed have been reported in the literature. However, if a participant develops unexpected side-effects, the study center (Radboudumc) can deliver adequate medical support of emergencies.

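### Section 4.4 turns a failure to prove value into a conclusion of no value, with no inconclusive outcome and no interval that could tell the two apart

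*Combined protocol and SAP*

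**What the plan says.** Section 4.4 gives the main purpose as establishing whether the scan is feasible and valuable as a way of assessing PSMA expression without tissue sampling. It says a sample size calculation does not apply because uptake data in these tumours are lacking, and it sets 15 ACC and 10 SDC patients. It closes with: "If the technique does not prove its value in these patients, we will conclude that it is not a valuable imaging technique", worded for ACC/SDC patients together. Section 8.5 replaces withdrawn patients until each histology has its own number of completers.

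Other sections bear on what value means:

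- Section 8.1.1 has a decision statement: "If the SUV of tumor tissue is higher than the SUV of healthy salivary gland tissue and/or comparable to the SUV in prostate cancer", expression is deemed sufficient to go on to a therapeutic study.
- Section 1, after saying that PSMA expression must be established on the scan to decide on eligibility for therapy, adds "This is the goal of this study". Section 11.4 says "If the study is successful, participants may participate in a therapeutic study".
- Section 13.1 (item a) speaks of imaging value: "There are several reasons why this could be a valuable imaging modality for these patients".
- Section 13.1 (item i) says SUV will be correlated with immunohistochemistry "to establish whether the efficacy of PSMA-PET imaging can be predicted with immunohistochemistry".

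For analysis, section 10.1 gives the SUV formula and the image processing. Section 10.2 says of the SUV ratios: "It will be presented as mean and standard deviations". The only named inferential analysis is the linear regression relating SUV to immunohistochemical expression, followed by a significance level of 0.05.

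**The concern.** A study can end in three ways: value shown, value excluded to a useful degree, or neither. Section 4.4 merges the last two and labels both as lack of value. With 10 and 15 patients the undecided range is wide, so the label would often be unsupported if results fell in the middle.

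Two features add to this. First, nothing in section 10 would let a reader undo the label, because no interval is planned for tumor SUV or for either ratio. Second, the sentence covers both histologies and no section sets out separate verdicts. If it were applied jointly and the histologies differed, the verdict would be wrong for one of them.

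At stake is the published conclusion. Section 1 makes this study the step before a therapeutic study with 177Lu-PSMA in diseases with few options. An unsupported negative statement could discourage that step.

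**Working it through.** **The plan's own figure.** The 15 + 10 = 25 patients come with no effect size, standard deviation, power or margin, so there is nothing to reproduce. The calculations below show only what these numbers can and cannot exclude. All proportions, counts and correlations are assumed.

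**1. Which result would show value?** Set side by side, the sections offer two candidates, and section 4.4 refers to neither.

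- *The SUV statement in 8.1.1.* It decides on a therapeutic study. It has no rule for combining patients and no figure for the prostate cancer comparison.
- *The correlation of SUV with immunohistochemistry.* It fits the wording of 4.4 about assessing PSMA expression. The Summary lists it among the main endpoints and section 8.1.2 among the secondary ones. The purpose given in 13.1 runs the other way: whether tissue staining predicts the scan.

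**2. Precision of a mean SUV or mean ratio.** The 95% half-width in units of the standard deviation is t(0.975, n−1)/√n.

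- SDC, n = 10: 2.262/√10 = 0.72 SD
- ACC, n = 15: 2.145/√15 = 0.55 SD

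**3. Precision if results were a proportion of patients** (exact Clopper-Pearson 95% limits).

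| Result | 95% interval |
|---|---|
| 5/10 | 18.7% to 81.3% |
| 7/15 | 21.3% to 73.4% |
| 1/10 | 0.3% to 44.5% |
| 3/15 | 4.3% to 48.1% |

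The first two rows exclude little. The last two put the proportion below one half, so a clear negative is reachable at these sample sizes.

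**4. Precision if value were judged by the correlation.** Fisher's transformation gives tanh[atanh(r) ± 1.96/√(n−3)]. It is approximate here because expression is scored on four points. For an observed r = 0.5:

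- n = 10: −0.19 to 0.86 (significance needs |r| of at least 0.632)
- n = 15: −0.02 to 0.81 (needs at least 0.514)
- n = 25: 0.13 to 0.75 (needs at least 0.396)

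Within either histology, r = 0.5 would count as not proven while remaining compatible with a strong correlation. The problem therefore does not depend on which candidate defines value.

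**5. If the sentence is read as one verdict.** Suppose 12/15 ACC (51.9% to 95.7%) and 1/10 SDC (0.3% to 44.5%). The intervals do not overlap. Pooled, 12 + 1 = 13 of 25 gives 31.3% to 72.2%, which looks middling and describes neither group.

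**6. How likely is a middling or low result?** The only rates in the documents are immunohistochemical: 85% in ACC, 70% in recurrent ACC, and above 80% in SDC (section 1). Treating these as uptake rates, which is an assumption, binomial tails give:

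- P(7 or fewer of 15) = 0.050 at 70% and 0.0006 at 85%
- P(5 or fewer of 10) = 0.033 at 80%

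**The case against.** The strongest reply is that this is one sentence in the sample size section of a small descriptive study. Section 10 contains no such rule, the therapeutic decision has its own statement in 8.1.1, and on the staining rates in the introduction a poor result is unlikely. That stands as a limit on the practical consequence. It does not rescue the sentence, which matters only when results disappoint and is then unsound. Section 13.1 (item i) itself calls the effect in ACC and SDC not yet predictable.

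A second reply is that ACC/SDC is the protocol's shorthand and may mean either histology, as it must in the inclusion criterion of section 4.2. That also stands. A reader might infer that the plan commits to pooling the histologies, but no section says so. The most that can be said is that the wording allows a joint verdict and nothing rules it out.

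A reader might also infer that the protocol gives value no meaning or has no decision criterion at all. The documents do not support this. Section 4.4 gives value an object, the assessment of PSMA expression, and 8.1.1 has a criterion for the therapeutic decision. What is missing is the link from 4.4 to a planned result. Nor do the documents settle which result it should be. Tying value to 8.1.1 could label a scan that correctly shows low expression as worthless.

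**Conclusion.** The concern holds as a defect in the conclusion rule. As written, section 4.4 would give a negative conclusion on a middling result that 10 or 15 patients cannot support, and the planned analysis offers no interval or test of the SUV or its ratios to correct it. The lack of a formal sample size calculation is not itself an error in an exploratory study; the error is attaching a firm negative conclusion to it.

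The size is modest. A reader might take the binomial figures as error rates of the plan, but the plan defines no proportion and no threshold, so none can be attributed to it. They illustrate precision under assumed results. If uptake followed the staining rates, the practical risk would be small. Staining positivity is not uptake, however, so this reassurance is itself an assumption. A clearly low result would still justify a negative conclusion. The change is worth making because it costs little and alters what the report may claim.

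**What to change.** Replace the last sentence of section 4.4 with:

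> Results will be reported for ACC and SDC separately, with 95% confidence intervals for tumor SUV, the tumor-to-background ratio and the tumor-to-healthy-salivary-gland ratio. If value is not shown in a histology, we will conclude that value was not demonstrated in this sample; we will conclude that the technique is not valuable in that histology only if the confidence interval excludes a useful result.

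Sections 10.1 and 10.2 should list the same intervals. Before the first scan the sponsor should state which result defines value and what level counts as useful. If the correlation with immunohistochemistry is chosen, it needs an interval too. A per-patient proportion with an exact interval is one option, not a requirement.

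The cost is a short change of wording, one definition fixed in advance, and intervals on data already collected. No patients or procedures are added. The sponsor would need to judge whether it is a substantial amendment under section 12.3.

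The downside is that an inconclusive result becomes possible, and a strict threshold rule could make it common even for a poor technique. For example, take a 35% threshold and a true proportion of 10%. Exclusion would need 0 of 10 in SDC, so about 1 − 0.9^10 = 65% of studies would be inconclusive. In ACC it would need at most 1 of 15, so about 1 − (0.9^15 + 15 × 0.1 × 0.9^14) = 45% would be. That is a reason to leave the form of the rule to the sponsor.
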